#### **2.1.4.2 Deaths**

The deaths observation period is per the observation periods defined above.

- Death on-study: deaths occurring during the on-study observation period.
- Death on-treatment: deaths occurring during the TEAE period.
- Death post-study: deaths reported after the last planned protocol visit.

#### **2.1.4.3 *Laboratory safety variables***

The clinical laboratory data consist of urinalysis and blood analysis.

Blood samples for laboratory tests are drawn at screening visit, Week 4 (except HbA1c), Week 8 (only for liver panel), Week 12, Week 24, Week 48, Week 72, Week 96 and EOT/EOS. Hepatitis B antigen is measured at screening only and Hepatitis C antibody at screening and at EOT/EOS. Serum pregnancy test is performed at screening and urine pregnancy test is performed at inclusion and at the end of study.

- Hematology (red blood cells [RBC] count, hemoglobin, hematocrit, platelets, white blood cells [WBC] count with differential blood count).
- Standard chemistry (fasting plasma glucose, sodium, potassium, chloride, bicarbonate, CPK, calcium, phosphorous, urea nitrogen, creatinine and calculated creatinine clearance using Cockcroft-Gault formula or Estimated Glomerular Filtration Rate [eGFR] using modification of the diet in renal disease (MDRD) Study equation, uric acid, total protein, lactic dehydrogenase (LDH), albumin,  $\gamma$ -Glutamyl Transferase [ $\gamma$ GT] Hepatitis B antigen, Hepatitis C antibody).
- HbA1c.
- Liver panel (ALT, aspartate aminotransferase [AST], alkaline phosphatase [ALP], and total bilirubin).
- Serum and urine pregnancy test.

Urinalysis - dipstick is performed at site or at the local Laboratory at screening, inclusion, Week 12, EOT/EOS visits and as needed during the study at investigator's discretion. It will assess for WBC, RBC, pH, specific gravity (qualitative/quantitative), and for the presence of blood, protein, glucose, ketones, nitrates, leukocyte esterase, uro-bilinogen and bilirubin.

Technical formulas are described in [Section 2.5.1](#).

#### **2.1.4.4 *Vital signs variables***

Vital Signs parameters include Weight, Heart Rate (HR), Systolic and Diastolic Blood Pressure (SBP and DBP) in sitting position.

#### **2.1.5 *Patient reported outcome***

The SIAQ©v2 (Self-Injection Assessment Questionnaire) is a Patient Reported Outcome (PRO) designated to assess the benefits and the potential limitations of self-injections of a subcutaneous medication perceived by patients who self-inject. It contains two modules; one to be self-completed before the first self-injection (hereafter "PRE module" or "PRE-SIAQ") and another one to be self-completed after self-injection (hereafter "POST module" or "POST-SIAQ").

- The PRE-SIAQ consists of 7 items grouped into three domains:
  - Feelings about injections (3 items),
  - Self-confidence (3 items),
  - Satisfaction with self-injection (1 item).

- The POST-SIAQ consists of 21 questions corresponding to 27 different items grouped into six domains:
  - Feelings about injections (3 questions/items),
  - Self-image (1 question/item),
  - Self-confidence (3 questions/items),
  - Injection-site reactions (2 questions including 8 items),
  - Ease of use (5 questions/items),
  - Satisfaction with self-injection (7 questions/items).

The PRE-SIAQ is completed only once by patients who self-inject, before the first self-injection and the POST-SIAQ is completed by any patient who self-injects at Week 4, Week 8, Week 12, Week 24, Week 48 and then at Week 72 and at Week 96.

See [Appendix B](#) for a more detailed presentation of the SIAQ©.

## 2.2 DISPOSITION OF PATIENTS

This section describes patient disposition for both patient study status and the patient analysis populations.

- Screened patients are defined as any patient who signed the informed consent.
- Enrolled patients consist of all screened patients, with a treatment kit number allocated and recorded in the interactive voice response system (IVRS)/interactive web response system (IWRS) database, regardless of whether treatment kit was used or not.

For patient study status, the total number of patients in each of the following categories will be presented in the clinical study report using a flowchart diagram or summary table:

- Screened patients.
- Screen failure patients and reasons for screen failure.
- Enrolled patients.
- Enrolled but not treated patients and reason for not being treated.
- Enrolled and treated patients.
- Patients who did not complete the study treatment period as per protocol.
- Patients who discontinued the study treatment by main reason for permanent treatment discontinuation.
- Status at last study contact.

For all categories of patients (except for the screened categories) percentages will be calculated using the number of enrolled patients as the denominator. A listing of other reasons for treatment discontinuation will be provided.

The incidence of premature treatment discontinuation (irrespective of the reason) and premature treatment discontinuation due to AEs will be presented graphically, using Kaplan-Meier method (provided that the number of patients concerned is not too small).

The disposition of patients will be presented overall and by country or pooled countries.

A patient is considered **lost to follow-up** (LTFU) if the patient has the information box “*Lost to Follow-Up*” ticked in the CRF p.46.

**All critical or major deviations** potentially impacting efficacy analyses, enrollment, and drug-dispensing irregularities, and other major or critical deviations will be summarized in tables giving numbers and percentages of deviations. The deviations are listed in the data review and surveillance plan.

In addition, the following populations will be summarized overall:

- Modified intent-to-treat population (mITT).
- Safety population.
- Self-injection population: safety population patients who gave themselves at least 1 alirocumab injection during the observational period.

Definition of the study population are given in [Section 2.3](#).

### **2.2.1 Enrollment and drug dispensing irregularities**

This is an open-label study and every patient will receive alirocumab. Treatment kit numbers will be allocated via interactive voice/web response system (IVRS/IWRS).

Each alirocumab treatment kit will be prepared to contain 6 pre-filled pens.

In addition to the alirocumab treatment kits, a training kit containing 1 placebo pre-filled pen will be prepared for the purpose of instructing patients on injection administration. The content of the labelling is in accordance with the local regulatory specifications and requirements.

Enrollment and drug-dispensing irregularities will be monitored throughout the study and reviewed on an ongoing basis. They will be documented in the clinical study report. The irregularities will be categorized and summarized among enrolled patients (number and percentages).

Enrollment and drug-dispensing irregularities to be prospectively identified include but are not limited to:

- Kit dispensation without IVRS transaction.
- Erroneous kit dispensation.
- Kit not available.
- Enrolled by error.
- Patient enrolled twice.

## 2.3 ANALYSIS POPULATIONS

### 2.3.1 Efficacy population

The efficacy population considered for efficacy analyses will be the mITT population.

The modified intent-to-treat population (mITT) also referred as on-treatment in section above, is defined as: all enrolled patients who took at least one dose or part of a dose of alirocumab and had an evaluable efficacy endpoint during the efficacy treatment period. The main efficacy endpoint will be evaluable provided that the 2 following conditions are met:

- Availability of a baseline calculated LDL-C value (last value available prior to the first injection of alirocumab).
- Availability of the calculated LDL-C within the analysis window associated to Week 12.

The efficacy treatment period is defined as the time period from the first injection of alirocumab up to the day of last injection + 21 days.

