STATISTICAL CONSIDERATIONS	
Sample size determination: No formal sample size calculation is performed. The table below displays the 95% Confidence intervals (95%CI) associated to a variety of adverse event rates for a targeted sample size of 1300 patients.
 

Adverse event rates	10%	20%	30%	40%	50%	

95%CI	[8.4%; 11.6%]	[17.8%; 22.2%]	[27.5%; 32.5%]	[37.3%; 42.7%]	[47.3%; 52.7%]	

 
For a rare non observed event, by using the rule of three, it can be estimated that the upper limit of the 95% confidence interval of the event rate is approximately 0.23% (1 per 433).
 
Analysis population: Safety population: all enrolled patients who actually received at least one dose or partial dose of alirocumab.
 
Efficacy population: Modified Intend To Treat population (mITT): all enrolled patients who received at least one dose or partial dose of alirocumab, with a baseline LDL-C value available and with at least one on-treatment LDL-C measurement during the efficacy treatment period.
 
Primary analysis: Safety analysis (adverse events, laboratory, product complaints and vital signs) will be performed on the safety population. Only descriptive summaries will be provided. The number of adverse events (AEs) during the study will be displayed. Adverse event incidence tables will present, by system organ class (SOC) high level group term (HLGT), high level term (HLT) and preferred term (PT), the number (n) and percentage (%) of patients experiencing an AE.
 
Secondary analysis: The effects of alirocumab will be documented by the proportion of patients reaching calculated LDL-C <100 mg/dL (2.59 mmol/L) at Week 12, the proportion of patients reaching calculated LDL-C < 70 mg/dL (1.81 mmol/L) at Week 12 as well as by values and percent changes from baseline in LDL-C, non-HDL-C, total-C, HDL-C, and TG levels after 12 weeks of treatment and at other time points. A descriptive analysis of the SIAQ will be done on the safety population. More details regarding statistical analyses will be provided in the SAP.
	Adverse event rates	10%	20%	30%	40%	50%	95%CI	[8.4%; 11.6%]	[17.8%; 22.2%]	[27.5%; 32.5%]	[37.3%; 42.7%]	[47.3%; 52.7%]
Adverse event rates	10%	20%	30%	40%	50%								

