#### **10.1.2.3 Visit 5 / Week 4 (Day 29 ±3), Visit 6 / Week 8 (Day 57 ±3), Visit 7 / Week 12 (Day 85 ±3), Visit 9 / Week 24 (Day 169 ±5), Visit 11 / Week 48 (Day 337 ±7), Visit 13 / Week 72 (Day 505 ±7), Visit 15 / Week 96 (Day 673 ±7)**

During these visits the below will be performed:

- Collect AEs.
- Check product complaints.
- Check compliance on IMP (review patient diary and treatment kit) and data collection on IMP administration.
- Record concomitant medication.
- Perform physical examination.
- Take vital signs including HR and BP.
- Urinalysis (only at V7).
- Laboratory tests: Hematology, Biochemistry, Liver panel, Lipid profile (hematology and biochemistry not needed for V6), HbA1c (except at V5 and V6).

- Remind Nutritional Counseling (including reviewing patient's diet).
- Provide any injection training reminder as needed.
- IVRS contact for treatment kit dispensing (at V5 and V6, new treatment kit dispensing would be done as per titration needs).

Reminders:

- An appointment will be given for the next study site visit, to be done before next IMP administration.
- Remind patient to be in fasting conditions (ie, overnight, at least 10 to 12 hours fast and refrain from smoking) for next study site visit. Also, alcohol consumption within 48 hours and intense physical exercise within 24 hours preceding the next study site visit are discouraged.
- Ask the patient to complete the SIAQ POST (ie, after alirocumab injection).
- Patient to bring the diary to the next study site visit.
- If upon review of the laboratory blood test results, the investigator judges that a dose titration of the patient dose is necessary, then he/she will contact the patient and plan an unscheduled visit. The assessments of the unscheduled visit will be at minimum the same of the "dispensation only" visit (eg, V10/Week 36).

**10.1.2.4 Dispensation visits: Visit 10 / Week 36 (Day 253 ±7), Visit 12 /Week 60 (Day 421 ±7), Visit 14 / Week 84 (Day 589 ±7), Visit 16 / Week 108 (Day 757 ±7)**

During dispensation visits the below will be performed:

- Treatment compliance will be checked.
- Patient' diaries will be reviewed.
- Safety and concomitant medication will be reviewed.
- Check product complaints.
- Provide any injection training reminder as needed.
- Treatment kit dispensing.

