## 11.3 ANALYSIS POPULATIONS

### 11.3.1 Efficacy population

#### 11.3.1.1 *Modified intent-to-treat population*

Modified intent-to-treat population (mITT): all enrolled patients who took at least one dose or part of a dose of alirocumab and had an evaluable efficacy endpoint during the efficacy treatment period. The main efficacy endpoint will be evaluable provided that the two following conditions are met:

- Availability of a baseline calculated LDL-C value (last value available prior to the first injection of alirocumab).
- Availability of at least one calculated LDL-C value during the efficacy treatment period and within one of the analysis windows up to Week 12.

The efficacy treatment period is defined as the time period from the first injection of alirocumab up to the day of last injection +21 days.

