The definition of the modified intent-to-treat (mITT) population was slightly changed in order to take into account the fact that no imputation will be performed for the missing LDL-C values. Consequently, the availability of a calculated LDL-C value within the analysis window associated to Week 12 is required (See [Section 2.3.1](#)).

In the SIAQ© population is included the condition of the patient who followed the training injection.

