### **2.1.3.2 Secondary efficacy endpoint(s)**

The main efficacy secondary endpoint will be:

- The percent change in calculated LDL-C from baseline to Week 12 (on-treatment estimand).

The key secondary efficacy endpoints will include:

- The proportion of patients reaching calculated LDL-C <100 mg/dL (2.59 mmol/L) at Week 12 (on-treatment estimand).
- The proportion of patients reaching calculated LDL-C <70 mg/dL (1.81 mmol/L) at Week 12 (on-treatment estimand).
- The proportion of patients with LDL-C <70 mg/dL (1.81 mmol/L) and/or ≥50% reduction from baseline in calculated LDL-C at Week 12 (on-treatment estimand).
- The percent change in non-HDL-C, total-C, HDL-C, TG from baseline to Week 12 (on-treatment estimand).

The other secondary efficacy endpoints will be:

- The proportion of patients who were up-titrated from 75 mg Q2W to 150 mg Q2W of alirocumab during the observational period based on investigator's judgment (on-treatment estimand).
- The proportion of patients who were down-titrated from 150 mg Q2W to 75 mg Q2W of alirocumab during the observational period based on investigator's judgment (on-treatment estimand).
- The reasons (ie, LDL-C threshold, AE) that triggered a down-titration or an up-titration of alirocumab (on-treatment estimand).
- The percent change in LDL-C from baseline over time, using all LDL-C values during the efficacy treatment period (on-treatment estimand) defined in [Section 2.3.1](#).
- The absolute change in calculated LDL-C (mg/dL and mmol/L) from baseline over time, using all LDL-C values during the efficacy treatment period (on-treatment estimand).
- The proportion of patients reaching calculated LDL-C <100 mg/dL (2.59 mmol/L) over time (on-treatment estimand).
- The proportion of patients reaching calculated LDL-C <70 mg/dL (1.81 mmol/L) over time (on-treatment estimand).
- The proportion of patients with calculated LDL-C <70 mg/dL (1.81 mmol/L) and / or ≥50% reduction from baseline in calculated LDL-C over time (on-treatment estimand).
- The percent change in non-HDL-C, total-C, HDL-C, TG from baseline over time (on-treatment estimand).
- The absolute change in non-HDL-C, total-C, HDL-C, TG (mg/dL and mmol/L) from baseline over time (on-treatment estimand).

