Since the study duration for each participating country will depend on when alirocumab becomes commercially available and reimbursed, with a minimum duration of 12 weeks and up to a maximum of 120 weeks, the secondary efficacy endpoints associated to the lipid parameters will be also assessed at the following time points depending on countries: Weeks 4, 8, 12, 24, 48, 72, 96 and 120 (EOT/EOS).

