##### ***2.4.4.2 Analyses of secondary efficacy endpoints***

Efficacy variables will be analyzed in the mITT population through descriptive statistics. No formal statistical comparisons will be performed for efficacy variables.

Quantitative descriptive summaries (number of available data, mean, SD, median, Min and Max) by planned time points will be presented for all lipids using observed (ie, non-missing) data. Missing data will not be imputed. In addition, standard error (SE) and the 95% CI for the mean will be provided for lipids other than TGs and Q1 and Q3 will be provided for TGs. The computation of the 95% CI will be based on a normal distribution or a Student distribution depending on the number of patients.

For all continuous secondary efficacy endpoints (LDL-C, non-HDL-C, total-C, HDL-C and triglycerides), percent changes from baseline using number of available data, mean, SD, median, Min, and Max will be displayed. For percent changes, 95% CI of the mean will also be provided.

The proportions of patients reaching the different targets defined for LDL-C (see [Section 2.1.3.2](#)) will be provided with their corresponding 95% CI. In case of a number of patients deemed insufficient, the Clopper-Pearson algorithm will be used to compute the 95% CI.

All measurements, scheduled or unscheduled will be assigned to analysis windows defined in [Section 2.5.4](#).

Regarding the patterns of up-titration/down-titration, the proportions with their corresponding 95% CI, will be provided for the following categories:

- Patients with at least one up-titration to 150 mg of alirocumab during the observational period. The time from the initiation of alirocumab at 75 mg to the first up-titration to 150 mg will be quantitatively described and the reasons that triggered the change of dosage will be displayed (AE, Lipid values or others).
- Patients with at least one down-titration to 75 mg of alirocumab during the observational period. The time from the initiation of alirocumab at 150 mg to the first down-titration to 75 mg will be quantitatively described and the reasons that triggered the change of dosage will be displayed (AE, Lipid values or others).
- Patients with a dose of alirocumab unchanged at 75 mg during the observational period and the duration of treatment without changes of doses.
- Patients with a dose of alirocumab unchanged at 150 mg during the observational period and the duration of treatment without changes of doses.

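### The SAP's mITT population requires a Week 12 LDL-C value, which needlessly removes on-treatment Week 4 and Week 8 data from patients who stop early

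*SAP*

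**What the plan says.** The documents give three versions of the LDL-C condition for the mITT population. All of them also require treatment and a baseline LDL-C.

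- Protocol synopsis: patients "with at least one on-treatment LDL-C measurement during the efficacy treatment period".
- Protocol Section 11.3.1.1: "Availability of at least one calculated LDL-C value during the efficacy treatment period and within one of the analysis windows up to Week 12".
- SAP Section 2.3.1: "Availability of the calculated LDL-C within the analysis window associated to Week 12".

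SAP Section 1.5 declares the last of these as a slight change, made "in order to take into account the fact that no imputation will be performed for the missing LDL-C values". Both documents end the efficacy treatment period 21 days after the last injection. SAP Table 3 sets the Week 12 window at days 71 to 98.

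The SAP defines no other efficacy population. Its Section 2.4.4.2 analyses efficacy variables in the mITT, and Section 2.1.3.2 lists eight lipid time points: "Weeks 4, 8, 12, 24, 48, 72, 96 and 120 (EOT/EOS". The same section classes the titration proportions as secondary efficacy endpoints, and they are analysed in Section 2.4.4.2. Section 2.4.4.4 (very low LDL-C, discontinuation of alirocumab, statin changes) is headed as additional efficacy analyses and names no population.

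**The concern.** One later measurement decides who is counted at every visit. A patient with a valid on-treatment LDL-C at Week 4 or Week 8, but none in the Week 12 window, leaves the Week 4 and Week 8 tables as well.

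The stated reason does not require this. Section 2.4.4.2 says that the quantitative summaries "will be presented for all lipids using observed (ie, non-missing) data", so a patient without a Week 12 value simply does not contribute at Week 12. Section 2.1.3.2 also defines the over-time LDL-C endpoints on all values in the efficacy treatment period, which a Week 12 condition on the population contradicts in practice.

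What is at stake is whether the early lipid tables describe all treated patients who were measured, or only those who were still being measured at Week 12. The titration proportions need no Week 12 LDL-C but inherit the condition. So do the Section 2.4.4.4 analyses, if they use the mITT.

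**Working it through.** **The plan's own precision figures.** With n = 1300 (SAP Table 1), the 95% half-width is 1.96 × √(p(1 − p)/1300). At 20% it is 2.2 points, giving 17.8 to 22.2. At 30% it is 2.5 points, giving 27.5 to 32.5. Both match the table. The documents give no expected mITT size and no missing-data rate.

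**Who cannot enter.** The opening sentence of SAP Section 2.3.1 requires the endpoint to be evaluable within the efficacy treatment period, so the Week 12 value must be on treatment. A value on day 71 or later then needs a last injection on day 71 − 21 = 50 or later. The Week 4 visit is day 29 ± 3 (days 26 to 32) and the Week 8 visit is day 57 ± 3 (days 54 to 60), from Protocol Section 10.1.2.3.

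| Last injection (day) | Period ends (day) | Week 4 visit on treatment | Week 8 visit on treatment | Day 71 reached |
|---|---|---|---|---|
| 1 | 22 | no | no | no |
| 15 | 36 | yes | no | no |
| 29 | 50 | yes | no | no |
| 43 | 64 | yes | yes | no |
| 57 | 78 | yes | yes | yes, days 71 to 78 only |

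Patients last injected on day 15, 29 or 43 therefore have usable scheduled data that the SAP discards. After a single injection, the final visit 14 to 21 days later (Protocol Section 10.1.2.5) falls on days 15 to 22, inside both the period and the Week 4 window. That value depends on the patient attending, so I do not count it as assured.

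**Later visits.** These early stoppers have no on-treatment values at Weeks 24 to 120. The only loss there is from patients who continue treatment without an LDL-C on days 71 to 98. The Week 12 visit is day 85 ± 3 (days 82 to 88), so a sample on day 99 would be at least 11 days late. Days 99 to 154 (56 days) belong to no window, so a late sample could not bring the patient back. This group is probably small.

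**Week 12 itself.** A patient restored by the protocol rule has no on-treatment Week 12 LDL-C and so adds nothing to the Week 12 LDL-C mean. SAP Section 2.5.3 leaves missing values out of percentages, so the target proportions do not move either. Total-C, HDL-C and non-HDL-C at Week 12 could change slightly: a patient without triglycerides has no calculated LDL-C but may have those values.

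**Possible size.** Let f be the share of protocol-mITT patients with no Week 12 value, and d their difference from the rest. The SAP figure then differs from the protocol figure by f × d. Both are assumptions.

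- f from 1% to 10% is 13 to 130 of 1300.
- Mean percent change at Weeks 4 and 8, with d from 0 to 20 points: 0 to 0.10 × 20 = 2.0 points.
- Titration proportions, with d from 0 to 30 points: 0 to 0.10 × 30 = 3.0 points.

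For scale, ODYSSEY COMBO I (Protocol Section 4) reports a standard error of 1.9 at Week 24 with 207 treated patients. That implies an SD near 1.9 × √207 = 27.3 and a half-width of 1.96 × 27.3/√1300 ≈ 1.5 points. This is another trial and a model-based error, so it is only a yardstick. At d = 20, f must exceed 1.5/20 = 7.5% for the shift to pass it. For titration at d = 30, f must exceed 2.2/30 ≈ 7.3% to pass the half-width at a 20% rate. Precision barely changes: at 50%, the half-width is 2.72 points with 1300 patients and 2.87 with 1170.

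**The case against.** The change is open. SAP Section 1.5 states it, and Protocol Section 11 allows the plan to be revised. The lipid objective concerns 12 weeks of treatment, and the main efficacy endpoint is at Week 12. Restricting to patients evaluable there gives a nearly fixed cohort, so Weeks 4, 8 and 12 are read on largely the same people. Other outputs cover part of the loss. LDL-C change is plotted among the safety analyses (SAP Section 2.4.5.3), which use the safety population. Discontinuation is reported on enrolled patients (Section 2.2). Section 2.4.4.4 lists every patient with a very low LDL-C.

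Much of this stands, and it lowers the weight of the point. A reader might infer an undisclosed conflict between protocol and SAP; Section 1.5 rules that out. A reader might infer that the main Week 12 LDL-C result is distorted by the new definition; it is the same under both.

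The fixed-cohort argument does not rescue the rule. The SAP does not offer it as the reason, and it makes the Week 4 and Week 8 results depend on a measurement taken later. The backstop is also weak: Section 2.4.1 repeats the baseline tables in the mITT only if that population falls below 90% of the safety population, so up to 130 of 1300 treated patients could be missing without triggering it.

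**Conclusion.** The point holds, with low severity. The SAP condition is narrower than the protocol's, the stated reason does not require it, and it discards valid on-treatment data, mainly at Weeks 4 and 8. The effect at Weeks 24 to 120 is secondary and probably small. It would overstate the case to say that all seven time points other than Week 12 suffer alike.

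Direction and size are unknown. Under the assumed ranges the shift is 0 to 2.0 points in mean percent change and 0 to 3.0 points in the titration proportions, and only the upper corner exceeds the confidence half-widths. Zero belongs in the range: the dropped patients were on treatment when sampled, and Protocol Section 8.1 expects the maximum LDL-C reduction by about Week 4.

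That titration and Section 2.4.4.4 use the mITT is inferred from how the SAP is laid out. A reader might go further and conclude that they belong on the safety population, but neither document assigns them there. All these analyses are descriptive, and the primary safety analysis is unaffected.

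**What to change.** - In SAP Section 2.3.1, restore the Protocol Section 11.3.1.1 condition: a baseline LDL-C plus at least one on-treatment LDL-C in a window up to Week 12.
- Keep observed data at each visit, so that only patients with a Week 12 value contribute at Week 12.
- Report how many treated patients lack a Week 12 value.
- State which population the titration and Section 2.4.4.4 analyses use. The restored mITT is enough. The safety population is an option, but it adds patients who stopped before a dose change was likely, which dilutes the titration proportions.

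The cost is SAP wording and one changed population flag, with no new data. Week 12 LDL-C tables stay as they are; Week 12 tables for the other lipids could change slightly.
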